Administration of intrathecal lipophilic opioid alone (fentanyl or sufentanil) has been shown to result in sufficient analgesia in the early phase of the labour without causing motor block of the lower limbs or drop of blood pressure due to blockade of the sympathetic neural system (4,5). This method is used routinely in our hospital with a spinal fentanyl dose of 25 micrograms. Until May 2013 our hospital routinely used sufentanil at a dose of 5 micrograms. Alternative option for the spinal opioid would be normal epidural analgesia where the local anesthetic dose is ropivacaine 20 mg and fentanyl 100 micrograms. The fentanyl dose of 100 micrograms could be replaced by sufentanil at a dose of 20 micrograms (6).

Purpose of the study

In this prospective randomized study the efficacy of spinal or epidural opioid (fentanyl or sufentanil) to alleviate the pain during contraction is studied. The opioid is given as a single treatment without any local anesthetics. The primary outcome for the study is the level of analgesia achieved in 20 minutes after the administration of the analgesia. The secondary outcomes are the rate of on-set of the analgesia measured by visual analog scale bar (VAS 0-100 mm; 100 mm worst possible pain; 0 mm no pain) from above 80 mm value (peak during contraction) to under 30 mm value and the duration of the analgesia provided by the neuraxial opioid alone.

Methods

Parturients

A total of 80 primiparous parturients will be recruited (20 parturients in each of the four treatment arms). According to the power calculation we expect to detect a potential difference

of 15 mm in the VAS scores at standard deviation of 15 mm with an 80 % certainty. Potential differences of less than 15 mm are not considered clinically relevant.

The parturients are ensured not to have any contraindications for spinal/epidural analgesia and they have not received any opioid analgesics by any route within 120 minutes prior to analgesia administration. The randomization is performed when the parturient asks for regional pain relief (i.e. spinal fentanyl according to the institutional practice). The delivery must be in the early phase marked by cervical dilatation of 5 cm or less at the time of the investigational analgesia and the pain VAS during contraction on the 0-100 mm VAS scale shall be at 80 mm or more. The BMI of the parturient at the date of delivery must be 20-35, the pregnancy singleton and the parturient may not have allergy for fentanyl, sufentanil or lidocaine. Furthermore, the parturient's ability to read and speak [Finnish](#) must be adequate so that she can understand the study and she can be interviewed according to the protocol after the analgesia.

The parturient will be given the study brochure prior to painful contractions reach the randomization level (VAS 80 mm). If the parturient agrees to participate in the study and fulfills the inclusion criteria, she will be randomized in to one of the four treatment arms.

Interventions

According to the randomization (20 parturients per group) the parturient is randomized to receive either fentanyl 20 micrograms intrathecally, fentanyl 100 micrograms epidurally, sufentanil 5 micrograms intrathecally or sufentanil 20 micrograms epidurally. The intrathecal medications are diluted according to the institutional protocol into the total volume of 2 ml and epidural medication is diluted into 5 ml volume by sterile saline.

Epidural analgesia is given through the epidural catheter and in all cases epidural catheter is flushed with 2 ml of saline at the end of procedure. The neuraxial analgesia procedure is performed according to the institutional protocol using Portex combined spinal epidural (CSE) set but for epidural drug administration the spinal needle is not used. In both intrathecal (spinal) and epidural medication groups, an epidural G18 catheter is left in the lumbar epidural space.

Blinding

For safety reasons the study will be blinded in such a manner that the parturient or the data collector do not know which analgesia is administered. The anesthesiologist providing the analgesia will prepare the sterile table and draw the medications outside the delivery room. The anesthesia chart will show the randomization code of the parturient. The key to the randomization codes is always available in the anesthesia office. Otherwise, the anesthesia report will be filled in a normal manner and the subsequent epidural analgesia boluses will be marked normally in the chart. The parturient is informed about the procedure using standardized phrases, which do not reveal the (spinal or epidural) nature of the analgesia provided for the midwife or the parturient. In both treatment groups an identical Portex epidural catheter remains in the back of the parturient.

Data will be collected after the drug delivery by another anesthesiologist who is blinded regarding the analgesia provided.

Follow up and data acquisition

The on-set of analgesia is monitored during each contraction on a 0-100 mm VAS scale for up to 30 minutes after the analgesia. The maximum achievable analgesia is expected to be achieved within 30 minutes. The fetal heartrate and the parturient's blood pressure is monitored for

30 minutes according to institutional protocol for neuraxial analgesia. Pruritus is the most common side-effect of the neuraxial opioids and it will be monitored by interview at 0, 10, 20 and 30 minutes. The used measurement scale is: 0 = no pruritus; 1 = mild pruritus; 2 = moderate pruritus; 3 =severe pruritus; 4 = unbearable pruritus. Potential nausea and vomiting will be documented at 0, 10, 20 and 30 minutes (for the past 10 minute interval). Also potential changes in the fetal heart rate, potential ob/gyn consultations and actions due to these consultations will be recorded.

Rescue analgesia and subsequent labour analgesia

The parturient can receive additional analgesia through the epidural catheter at the earliest 30 minutes after the spinal or epidural opioid administration. At 30-45 minutes after the intervention the parturient may get 20 mg ropivacaine in 20 ml saline, whereas after 45 minutes a dose of 20 mg of ropivacaine and 50 micrograms of fentanyl in 20 ml can be given.

Data to be collected in the trial

Background information (height, weight, duration of pregnancy)

from primary health care maternity chart

Gestational data (duration of pregnancy)

from the hospital Obstetrics software

Prior analgesia during delivery

from the hospital Obstetrics software

Pain VAS (0-100 mm) immediately prior to investigational analgesia and for each contraction thereafter for 30 minutes

Interviewed from the parturient

Pruritus and nausea at 0; 10; 20; 30 minutes after the analgesia

Interviewed from the parturient

Timing of the next epidural analgesic dose, cervical dilatation prior to the next epidural dose. Information on the analgesia provided by the epidural dose.

from the hospital Obstetrics software

Time of delivery, mode of delivery (cesarean delivery, vacuum assisted delivery), potential postpartum operations in the operating theatre.

from the hospital Obstetrics software

Fetal heart rate (FHR)

automatically registered into the hospital Milou system

Archival of the collected data, processing of personal information regarding parturients

The collected data will be archived at the Department of Anaesthesiology in a locked cabinet to which only the investigators have access. When the information is transferred into the electronic data file all directly identifying information will be removed (name and date of birth). The

study participants can be subsequently identified by matching case number with the signed consent form. No directly identifying information is saved in the electronic form.

Analysis of the collected data

For statistical analysis the information is transferred into SPSS software, which is used for comparison of the continuous data (background information, pain VAS scores) and categorical data (adverse events such as nausea, pruritus).

The primary outcome is measured in millimeters on a 100 millimeter line and processed as a continuous variable with 0 mm indicating no detectable pain and 100 mm indicating the worst possible pain. Similarly secondary outcome marker, the duration of analgesia, will be recorded in minutes and processed as a continuous variable. The incidence of adverse events will be recorded as presence or absence of certain adverse events (pruritus, nausea) and analyzed as a categorical variable.

Chi-squared test will be used for categorical variables while Kruskal-Wallis test for independent samples is used for comparisons of continuous variables between the treatment arms.

The fetal heartrate (CTG) recordings will be retroactively analyzed by an obstetrician for potential pathology prior to analgesia and for 30 minutes thereafter. The obstetrician is blinded regarding the intervention.

All data and events are analyzed according to original allocation into respective intervention groups.

Completion of the study

Recruiting of the parturients will begin once the required permits have been received. The parturients will be recruited during 2016 and the results of the study will be published in a peer reviewed journal thereafter. The study will be completed at Helsinki University Central Hospital /Katiolopisto delivery hospital without external sponsors or funding as part of normal quality improvement work.

Ethical considerations

The parturients will be recruited for the study at the very early phase of the labour. The institutional normal protocol is to give 25 micrograms of fentanyl intrathecally. The fentanyl dose used in this study (20 micrograms) does not differ in terms of efficacy from the 25 microgram dose and the efficacy of the other interventions is expected to be in the similar range. Epidural delivery of fentanyl or sufentanil alone without local anesthetic has not been previously studied in the early phase of the labour.

This study will provide information regarding possible replacement of spinal opioid administration with epidural opioid thus avoiding risks and limitations associated with spinal opioid delivery.

No placebo control is used in this study and the parturients will not be exposed to additional injections or painful maneuvers. It is possible that epidural analgesia does not have as fast on-set as spinal analgesia. The only viable option for spinal drug administration currently would be

epidural analgesia which is not routinely preferred at such early phase of the delivery. Therefore, the participating parturients are expected to receive at least as good labour analgesia as those parturients who do not participate in the trial.

References

2. Jenkins JG. Some immediate serious complications of obstetric analgesia and anaesthesia: a prospective study of 145.550 epidurals. *Int J Obstet Anesth* 2005; 14: 37-42.

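### The 80% power for 15 mm is tied to no named comparison, and the planned Kruskal-Wallis test cannot say whether the spinal and epidural regimens differ

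*Combined protocol and SAP*

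**What the plan says.** All references are to the combined protocol and SAP.

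- **Purpose of the study:** "The primary outcome for the study is the level of analgesia achieved in 20 minutes after the administration of the analgesia".
- **Methods, Parturients:** "A total of 80 primiparous parturients will be recruited (20 parturients in each of the four treatment arms". The detectable difference is given as one "of 15 mm in the VAS scores at standard deviation of 15 mm with an 80 % certainty", followed by "Potential differences of less than 15 mm are not considered clinically relevant". No pair of arms, pooled groups, test, alpha, sidedness or dropout allowance is given.
- **Interventions:** women receive "either fentanyl 20 micrograms intrathecally, fentanyl 100 micrograms epidurally, sufentanil 5 micrograms intrathecally or sufentanil 20 micrograms epidurally". This is a two-by-two layout of route and drug. Intrathecal doses are made up to 2 ml and epidural doses to 5 ml.
- **Analysis of the collected data:** "Kruskal-Wallis test for independent samples is used for comparisons of continuous variables between the treatment arms". No contrast, follow-up comparison, multiplicity rule, effect estimate or confidence interval is specified.
- **Ethical considerations:** the study is to inform "possible replacement of spinal opioid administration with epidural opioid", and "the efficacy of the other interventions is expected to be in the similar range".

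**The concern.** The power statement, the test and the stated use of the result do not connect. The power statement speaks of a difference without saying between what. The test compares arms without singling out any comparison. The use described under Ethical considerations concerns spinal against epidural administration.

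Two things are at stake. First, a reader cannot tell which comparison the 80% covers, or whether the planned test delivers it. Second, a four-arm p-value does not say whether route or drug is responsible, and it gives no estimate to hold against the 15 mm relevance limit. If efficacy is similar across arms, as the protocol expects, a non-significant result is likely, and it would leave the replacement question open.

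**Working it through.** **Inputs.** From Parturients: 20 per arm, four arms, difference 15 mm, SD 15 mm, power 80%. Assumed because not stated: two-sided alpha 0.05, no dropout, normal data with the same SD in every arm.

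**1. The plan's own figure, read as one two-arm comparison.**

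- Normal approximation: n = 2 × (1.960 + 0.842)² × (15/15)² = 15.7, so 16 per arm; the t-test needs 17.
- At 20 per arm, SE = 15 × √(2/20) = 4.74 mm and 15/4.74 = 3.16. Power is Φ(3.16 − 1.96) = 88.5%, or 86.9% by t-test and 84.8% by rank-sum test (simulated).

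The 80% is therefore met and exceeded. Exactly 20 per arm can also be reached by undocumented routes: alpha 0.025 (normal approximation), or the t-test size divided by the worst-case rank efficiency (16.7/0.864 = 19.3, so 20). If all six pairs were meant with a Bonferroni correction, power would be 64.8% (t-test) or 59.4% (rank-sum).

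**2. The same inputs in a four-arm test.** The noncentrality is λ = n × Σ(μᵢ − μ̄)²/SD², so power depends on where the other arms lie. Kruskal-Wallis power is simulated (chi-square, 3 df, 100,000 runs; rejection under the null 4.8%).

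| Arm means (mm) | Σ(μᵢ − μ̄)² | λ | ANOVA | Kruskal-Wallis |
|---|---|---|---|---|
| 0, 7.5, 7.5, 15 | 112.5 | 10.0 | 73.7% | 70.5% |
| 0, 5, 10, 15 | 125 | 11.1 | 78.6% | 75.6% |
| 0, 0, 0, 15 | 168.75 | 15.0 | 90.2% | 87.9% |
| 0, 0, 15, 15 | 225 | 20.0 | 96.8% | 95.9% |

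In the least favourable pattern, 80% is reached at a gap of about 16.6 mm instead of 15 mm.

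**3. Sensitivity to shape.** In the least favourable pattern, gamma data (an assumed shape) with a lowest arm mean of 30, 20, 15 or 10 mm give 77%, 83%, 88% or 95%. Normal data cut at 0 and 100 mm give 70%.

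**4. What a significant result would mean.** Order the arms as spinal fentanyl, spinal sufentanil, epidural fentanyl, epidural sufentanil. A pure 15 mm route effect is (0, 0, 15, 15), a pure drug effect is (0, 15, 0, 15), and a crossing interaction with no average effect of either is (0, 15, 15, 0). With equal arms, Kruskal-Wallis ignores the labels, so power must be identical for all three; simulation gave 95.9%, 96.0% and 95.8%.

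**5. What the same 80 women can give.** These figures use the plan's SD and a linear model with 76 residual df (t = 1.992).

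- Epidural minus spinal, 40 v 40: SE = 15 × √(2/40) = 3.354 mm; half-width 1.992 × 3.354 = 6.7 mm. Power is 99% for 15 mm and 80% for about 9.5 mm. Kruskal-Wallis needs about 11.7 mm to reach 80% for the same pure route effect. If the SD were 20 mm, the half-width would be 8.9 mm.
- Route difference within one drug, 20 v 20: SE = 15 × √(2/20) = 4.743 mm; half-width about 9.4 mm.
- Route-by-drug interaction: SE = 15 × √(4/20) = 6.708 mm; half-width 13.4 mm; power 60% for 15 mm.

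**The case against.** **The test may not be a single four-arm test.** The analysis section speaks of comparisons in the plural and does not say omnibus. Applied to two groups, Kruskal-Wallis is the rank-sum test, and one unadjusted pair has 85% power. This stands in part. The four-arm reading is the most natural one, but the text does not prove that only one p-value will be produced. What is certain is that no particular contrast or estimate is planned.

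**The shortfall depends on the model.** This stands. The documents give no arm means or distribution, and moderate skew lifts even the least favourable pattern above 80%. A reader might infer that the trial is underpowered or that the 80% is miscalculated; neither is supported.

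**A shortfall would need both drug and route to have average effects.** A reader might infer this, but it is true only without interaction. With spinal fentanyl at 0, epidural fentanyl at 15 and both sufentanil arms at 7.5 mm, the average drug effect is zero (7.5 against 7.5), yet these are the least favourable means and power is 71%.

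**Route is not the declared hypothesis.** The replacement sentence is a benefit statement under Ethical considerations, and 15 mm is a relevance limit. This stands to the extent that the trial should not be read as a non-inferiority study. The protocol still presents its results as informing that choice, and the analysis as written does not serve it.

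**A pooled contrast does not isolate route either.** This stands. Dose and volume differ between the spinal and epidural arms, so the contrast compares regimens as given.

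**Conclusion.** The concern holds as a mismatch between the power statement, the test and the stated use of the result. The power part is modest. The 80% is met for one unadjusted pair and is not assured for the four-arm test, where power is about 71% to 96% for a largest gap of 15 mm. That range rests on two-sided 0.05, normal data with SD 15 mm in every arm, and no dropout.

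The larger part does not depend on a power shortfall. A four-arm Kruskal-Wallis test responds equally to route, drug and crossing patterns, so significance would not show that the spinal and epidural regimens differ. Non-significance would not show that one can replace the other. The 80 women already planned are enough to estimate the regimen difference to about ±6.7 mm; the plan does not ask for that estimate. This should be fixed, and it gives no reason to enlarge the trial.

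**What to change.** Keep 80 women.

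1. **Analysis of the collected data.** Keep Kruskal-Wallis as the primary test, so that only one test is primary at the stated alpha, and add as a supporting estimate:

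   > The epidural minus spinal difference in 20-minute VAS (40 v 40, adjusted for drug) will be reported with its 95% confidence interval and read against the 15 mm relevance limit. The route-by-drug interaction and the within-drug route differences (20 v 20) will be reported beside it.

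   Describe it as a comparison of the spinal and epidural regimens as given, and do not call it a non-inferiority test.

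2. **Parturients.** State the comparison and alpha that the 80% refers to. If it is the four-arm test, replace the single figure with about 71% (two arms midway) to 96% (two arms against two), with the assumptions. If it is one two-arm comparison, name it and plan its test in the analysis section.

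**Cost.** Item 2 is wording only, but if the four-arm test is meant, the protocol then shows a floor below 80%. Item 1 is one added analysis with no new women or data. Its weakness is the interaction, estimated only to about ±13.4 mm, so a moderate one could be missed. The pooled estimate must therefore be read with the within-drug differences, which have a half-width of about 9.4 mm.

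### The primary 20-minute VAS comparison leaves out the pre-injection VAS the trial already records; a rank ANCOVA would recover a modest amount of precision

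*Combined protocol and SAP*

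**What the plan says.** - **Outcome.** Purpose of the study: "The primary outcome for the study is the level of analgesia achieved in 20 minutes after the administration of the analgesia". Analysis of the collected data adds: "The primary outcome is measured in millimeters on a 100 millimeter line and processed as a continuous variable". It is a level in mm; no change from baseline is defined.
- **Baseline.** Data to be collected in the trial lists "Pain VAS (0-100 mm) immediately prior to investigational analgesia and for each contraction thereafter for 30 minutes".
- **Test.** Analysis of the collected data: "Kruskal-Wallis test for independent samples is used for comparisons of continuous variables between the treatment arms". No adjusted analysis is named anywhere.
- **Entry.** Parturients: "the pain VAS during contraction on the 0-100 mm VAS scale shall be at 80 mm or more". Baseline can therefore lie only between 80 and 100 mm.
- **Size.** Parturients: "A total of 80 primiparous parturients will be recruited (20 parturients in each of the four treatment arms", planned for a difference "of 15 mm in the VAS scores at standard deviation of 15 mm with an 80 % certainty". Smaller differences are called clinically irrelevant. Alpha is not stated.

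**The concern.** A baseline reading of the outcome scale is usually the most useful covariate in a pain trial, and here it costs nothing to obtain. Kruskal-Wallis takes no covariate, so variation in 20-minute pain that the starting level could explain stays in the error term. With 20 women per arm, chance differences in starting pain also carry over in part to the 20-minute comparison. At stake are somewhat wider uncertainty than necessary and a primary result without an estimate in mm to set against the 15 mm limit. Choosing the adjustment in advance also prevents a choice between adjusted and unadjusted results once the data are seen.

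**Working it through.** **Inputs from the protocol:** 4 arms of 20, SD 15 mm, difference 15 mm, power 80%, baseline within 80-100 mm. **Assumed:** two-sided alpha 0.05; correlation r between baseline and 20-minute VAS; shape of the baseline distribution.

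**1. The plan's own figure.** For one pair of arms, n = 2 × (1.960 + 0.842)² × 15²/15² = 15.7, so 16 per arm (17 by t-test). At 20 per arm, 15/(15 × √(2/20)) − 1.960 = 1.202, which gives 88.5% power (86.9% by t-test). The stated 20 is reached if the t-test figure is divided by the worst-case efficiency of a rank test: 16.7/0.864 = 19.3. The figure is thus conservative for a single pair and is not shown to be wrong.

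**2. How large r can be.** On an 80-100 mm band the baseline SD cannot exceed 10 mm. It is 20/√12 = 5.8 mm if uniform, and 5.3-5.6 mm for the truncated normal shapes tried. Under those truncated shapes, an unrestricted r of 0.5 shrinks to 0.16-0.30, and 0.3 shrinks to 0.09-0.17. A range of 0.1 to 0.3 is therefore reasonable.

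**3. Variance saving.** Residual variance is multiplied by 1 − r², and the equivalent sample is 80/(1 − r²).

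| r | Saving | Residual SD (mm) | Equivalent N |
|---|---|---|---|
| 0.1 | 1% | 14.92 | 80.8 |
| 0.2 | 4% | 14.70 | 83.3 |
| 0.3 | 9% | 14.31 | 87.9 |

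Estimating one slope costs a factor of about 1 + 1/74 = 1.0135. The net gain in a linear model starts where 1 − r² < 1/1.0135, that is, above r of about 0.12. At r = 0.3 the half-width of a pairwise 95% interval goes from 1.99 × 15 × √(2/20) = 9.4 mm to 9.4 × √0.91 = 9.0 mm, before that small cost.

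**4. Chance imbalance.** With baseline SD 5.8 mm, a two-arm baseline difference has SD 5.8 × √(2/20) = 1.8 mm. It passes through multiplied by the slope, r × 15/5.8, which is 0.5 at r = 0.2 and 0.8 at r = 0.3. That is about 1 to 1.4 mm.

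**5. Power of the four-arm test, by simulation.**
- *Normal data, two arms 15 mm apart and two midway.* At r = 0, rank ANCOVA and Kruskal-Wallis both had 70.0%. At r = 0.2-0.3 rank ANCOVA gained about 1 to 4 points. Type I error stayed near 5%.
- *Normal data, one arm shifted by 15 mm.* Kruskal-Wallis against rank ANCOVA: 88.9% and 89.2% at r = 0.1; 87.9% and 89.1% at 0.2; 87.7% and 90.5% at 0.3.
- *Skewed data near the floor (gamma shape, SD 15, arm means 12.5/20/20/27.5 mm).* At r = 0, rank ANCOVA had 91.5% and Kruskal-Wallis 91.6%. At r = 0.2-0.3, linear ANCOVA had about 76-77% against 90-92% for Kruskal-Wallis.

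**The case against.** The best defence of the plan is that a rank test is a sensible choice here. The onset outcome looks for a fall from above 80 mm to under 30 mm, so many 20-minute scores may sit near zero and be right-skewed. Randomisation keeps the unadjusted test valid, the entry floor leaves little baseline variation to exploit, and r is unknown. All of this stands. It limits the size of the point and rules out one remedy, but it does not justify leaving the baseline unused, since rank adjustment keeps the robustness and costs essentially nothing at r = 0.

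A reader might go further in three ways that the documents do not support.

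- **That linear ANCOVA should replace the rank test at no risk.** Step 5 shows a loss of roughly 15 points under one plausible skewed shape. On normal data, some 2-3 points of its advantage over Kruskal-Wallis come from normality and not from baseline.
- **That the planned test misses the stated 80% power and adjustment repairs this.** The figure of about 70% belongs to the least favourable layout, with two arms midway. The protocol specifies only a potential 15 mm difference. With one arm shifted, Kruskal-Wallis has about 88-89%, and a single pair by t-test or normal approximation has 87-89%.
- **That baseline imbalance passes in full into the result.** Step 4 shows that only about 1 to 1.4 mm does, against a 15 mm limit.

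Differences in mm with intervals could also be reported without adjustment, so that benefit does not depend on this point.

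**Conclusion.** The point holds as a modest efficiency improvement. The trial collects the pre-injection VAS, and the stated primary comparison does not use it. The comparison remains unbiased and the test valid. At an assumed r of 0.1 to 0.3, the saving is about 1% to 9% of variance, or about 1 to 8 women of 80, and about 0 to 4 power points, with essentially no loss for rank ANCOVA at r = 0. These figures rest on an assumed correlation, an assumed two-sided alpha of 0.05, the protocol's SD of 15 mm and simulated outcome shapes; the documents give neither the correlation nor the shape. The adjustment should not be presented as curing a shortfall from 80% power.

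**What to change.** In Analysis of the collected data, before unblinding:

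1. Make the primary analysis of the 20-minute VAS a rank ANCOVA (Quade) across the four arms, with the pre-injection contraction VAS as covariate: rank both variables over all women, regress the outcome ranks on the baseline ranks, and compare the residuals between arms.
2. Keep the unadjusted Kruskal-Wallis test as a sensitivity analysis.
3. Report baseline-adjusted differences in mm between arms with 95% confidence intervals as supporting estimates, to be read against the 15 mm limit.

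The cost is a few lines of analysis text and one estimated slope. It needs no new data, staff or participants, and SPSS, the named software, can run it.

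### Duration of analgesia is to be tested as a complete continuous variable, but a woman who delivers or has a caesarean without a further epidural dose has no recorded end time, and the plan gives no rule for her

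*Combined protocol and SAP*

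**What the plan says.** Under Purpose of the study, one secondary outcome is "the duration of the analgesia provided by the neuraxial opioid alone". No start, end or event is defined for it there or elsewhere.

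Under Analysis of the collected data:
- "Similarly secondary outcome marker, the duration of analgesia, will be recorded in minutes and processed as a continuous variable".
- "Kruskal-Wallis test for independent samples is used for comparisons of continuous variables between the treatment arms".
- "All data and events are analyzed according to original allocation into respective intervention groups".

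Under Data to be collected in the trial, three items bear on when analgesia ends:
- "Pain VAS (0-100 mm) immediately prior to investigational analgesia and for each contraction thereafter for 30 minutes".
- "Timing of the next epidural analgesic dose, cervical dilatation prior to the next epidural dose".
- "Time of delivery, mode of delivery (cesarean delivery, vacuum assisted delivery"), with the time and mode of delivery not linked to duration.

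The section on rescue and later labour analgesia sets the first possible time of a further dose: "The parturient can receive additional analgesia through the epidural catheter at the earliest 30 minutes after the spinal or epidural opioid administration".

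The plan contains no censoring rule, no missing-data rule and no time-to-event method.

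**The concern.** Duration here is in practice a time to an event that need not happen. If labour ends before another dose is given, all that is known is that the opioid lasted at least until then. Kruskal-Wallis ranks one finished value per woman and has no place for a value known only to exceed some time.

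The analyst then has two obvious choices: leave the woman out, or enter her time to delivery as though analgesia ended at that moment. Both lose information from the long end of the distribution. The longer an opioid works, the more often labour ends first, so a longer-acting arm loses more. At stake is an understated difference between arms in a named efficacy outcome, and a choice of handling made after the data have been seen.

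**Working it through.** **Plan's own figure.** None is given for duration. The stated 20 per arm belongs to the pain score (15 mm difference, SD 15 mm, 80% power). With two-sided alpha 0.05 (assumed), n = 2 × (1.96 + 0.84)² × (15/15)² = 15.7, so 16 per arm. The t-test version gives 17, and allowing for rank-test efficiency of 0.955 or 0.864 gives 18 or 20. The figure is reproduced and does not bear on this point.

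**Which item can end the duration.** Pain scores cover minutes 0 to 30, and a further dose is possible from minute 30. Any end after minute 30 can therefore come only from the timing of the next dose. Time of delivery is collected and can serve as a censoring time.

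**Size, first illustration.** The documents give neither durations nor times to delivery, so every input here is assumed. Duration is lognormal with median m = 110 or 85 minutes and log-SD 0.4. Time to delivery is lognormal with median D and log-SD 0.6, independent of arm and of duration.

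- True mean = m × exp(0.4²/2) = 1.083m, giving 119.2 v 92.1, a difference of 27 minutes.
- Share with no next dose = Φ[ln(m/D) / √(0.4² + 0.6²)]. For m = 110 and D = 200: ln(0.55) = −0.598, divided by 0.721 = −0.829, and Φ = 0.20.
- The two mean differences below were simulated: first with women lacking a next dose left out, then with the smaller of duration and time to delivery entered for each woman.

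| D (min) | No next dose, 110 v 85 arm | Expected per 20 women | Mean difference, left out | Mean difference, delivery time entered |
|---|---|---|---|---|
| 200 | 20% v 12% | 4.1 v 2.4 | 22 | 21 |
| 250 | 13% v 7% | 2.5 v 1.3 | 23 | 23 |
| 300 | 8% v 4% | 1.6 v 0.8 | 24 | 25 |
| 480 | 2.0% v 0.8% | 0.4 v 0.2 | 26 | 26 |

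The mean differences only show the distortion on a scale of minutes. The planned test works on ranks.

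**Size, second illustration.** Here both duration and time to delivery equal 30 minutes plus a lognormal, reflecting the earliest further dose (log-SD of the duration part 0.5). Women without a next dose are left out.

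| True median (min) | D = 240, log-SD 0.7: lost; observed median | D = 480, log-SD 0.5: lost; observed median |
|---|---|---|
| 60 | 1%; 60 | 0%; 60 |
| 90 | 7%; 88 | 0.2%; 90 |
| 120 | 16%; 113 | 1%; 119 |
| 150 | 26%; 136 | 3%; 148 |

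Loss and shortening both rise with true duration, as expected.

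**Power, 20 per arm, four arms.**
- Second model, medians 90, 90, 120, 120, delivery log-SD 0.6. At D = 240: 0.84 if every duration were known, 0.77 for Kruskal-Wallis with women left out, 0.81 for log-rank with censoring. At D = 360: 0.85, 0.79 and 0.83.
- First model, medians 110, 110, 85, 85, Kruskal-Wallis with women left out v log-rank: 0.48 v 0.57 (D = 200), 0.52 v 0.59 (250), 0.57 v 0.59 (300), 0.60 v 0.62 (480).

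**The case against.** **The plan is silent; it does not exclude anyone.** A reader might infer that the planned test drops these women. No text says so, and the documents do not define duration as time to the next dose. This stands: the fault is a missing definition and rule combined with a method that needs complete values. The silence does not remove the problem, because both obvious ways of filling it distort in the same direction.

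**Leaving out a blank is not a breach of analysis by allocation.** A reader might infer a conflict with that sentence. It says which group a woman belongs to, and it does not say how a missing value is handled. Leaving her out moves nobody to another group, so that charge is not supported.

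**A surgical dose is not the listed item.** The data list speaks of an analgesic dose, so on a plain reading a dose given to start surgical anaesthesia would not count. This is a fair reading, but the plan does not spell it out, and a few words would settle it.

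**The effect may be negligible.** The women are primiparous and enter at 5 cm dilatation or less, so labours may be long. At an assumed median delivery time of 480 minutes, fewer than one woman per arm is affected and about 1 minute is lost. This stands as a limit on size. Even then, with two arms at each duration, the chance that at least one of 80 women lacks a next dose is 1 − 0.9795⁴⁰ × 0.9918⁴⁰ ≈ 0.69, so a rule would probably still be needed.

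**Conclusion.** The point holds as a cheap improvement. Duration is an incomplete time-to-event outcome assigned to a test for complete values, with no rule for women who have no further labour epidural dose.

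The direction, toward no difference between arms, rests on time to delivery being unrelated to arm and to duration. If a treatment changed the course of labour, the direction could differ. The size cannot be found from the documents. Under the assumed medians of 110 v 85 minutes, a 27-minute difference becomes about 21 to 25 minutes with median delivery at 200 to 300 minutes, and about 26 with 480. Nothing in the documents shows which range applies.

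A reader might extend this to the trial's main conclusion. That is not supported: the primary outcome is pain at 20 minutes, before any further dose is allowed, and neither it nor the sample size depends on how duration is handled.

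**What to change.** Under Analysis of the collected data, for this outcome only:

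1. Define duration as the time from the study injection to the next epidural dose given for labour analgesia, and state that a dose given for surgical anaesthesia is not the event.
2. Censor a woman with no such dose at delivery, using the time and mode already collected. For a caesarean, censor at the decision instead if that time is available in the record.
3. Replace Kruskal-Wallis by Kaplan-Meier curves and a log-rank test across the four arms, by original allocation.
4. Report the number censored in each arm.

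The cost is a short wording change and a routine procedure in SPSS. The time of the caesarean decision is not a listed data item; where it cannot be found, delivery time serves, at the price of counting a short interval under surgical anaesthesia as follow-up.

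There are limits. Censoring assumes that delivery is unrelated to the analgesia remaining. If that is doubted, delivery and caesarean can be treated as competing events, with cumulative incidence reported. The gain is small if labours are long. A duration defined by the next dose also cannot be shorter than the 30-minute wait that the plan sets for all arms.
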